2.2 Rationale and Objectives

IBS-C is a chronic medical condition with few treatment options. Many patients either fail to achieve an adequate response or cannot tolerate the existing treatments. Therefore, new treatment options that offer similar or better levels of clinical benefit are needed. Clinical studies of plecanatide in patients with IBS-C and CIC suggest that it is well-tolerated and may improve bowel frequency while decreasing abdominal pain.

The primary objective of this study is to evaluate the long-term safety and tolerability of plecanatide administered once daily for the treatment of IBS-C. In addition, patients' assessments of disease severity and adequacy of treatment will be collected. Desire for treatment continuation will be assessed for each patient at their last visit in the study.

2.2.1 Rationale for the Dose Selection

The once a day 6 mg dose of plecanatide selected for this study is based upon observations from prior plecanatide studies. Doses of 3 and 9 mg/day given for 12 weeks were shown to be safe and effective in a Phase 2 trial of patients with IBS-C, with 3 mg dose demonstrating clinically significant efficacy. The 6 mg daily dose is being evaluated in the core studies and is anticipated to provide desired efficacy with minimal treatment-related side effects. Administration of 6 mg plecanatide for longer-term treatment in this patient population is warranted and will support the highest intended dose in this indication.

2.3 Risk-Benefit Assessment

Based on previously completed clinical studies in patients with IBS-C and CIC, the anticipated benefits of treatment with 6 mg/day of plecanatide for 53 weeks are expected to outweigh the potential risks. Plecanatide has demonstrated no detectable systemic absorption (with a 1 to 10 ng/ml limit of detection). Moreover, the safety profile for 9 mg plecanatide administered daily for 12 weeks was quite acceptable; a dose of 6 mg is expected to be at least as safe and well tolerated. Study patients will be carefully monitored for TEAEs at scheduled study visits.

2.4 Criteria for Evaluation of the Study

The safety, tolerability and exploratory endpoints are described below. For information concerning the analyses of these endpoints, see Section 8.

2.4.1 Safety and Tolerability Endpoints

Safety and tolerability will be measured by the number and nature of treatment-emergent adverse events (TEAEs), serious adverse events (SAEs), withdrawals due to adverse events (AEs), treatment interruptions due to diarrhea or other AEs, AE-free days, and the percentage of patients remaining in the study at each week. Other clinically significant changes in vital signs, clinical laboratory assessments, physical examinations and ECGs will be assessed.

2.4.2 Exploratory Endpoints

Patients' assessments of disease severity and adequacy of treatment will be collected by self-administered questionnaires completed by the patient at every study visit, ideally prior to any other study assessments (see Appendix 1 for details).

2.5 Study Design

An open-label, single-arm design with up to 53 weeks of treatment with plecanatide 6 mg QD (the highest dose being evaluated in the core studies) was chosen in accordance with the ICH E1 exposure guideline for drugs intended for chronic use. This study will provide additional data related to the chronic use of plecanatide at the dose intended for clinical use in patients with IBS-C. (See Figure 1)

2.6 Planned Sample Size and Number of Study Centers

It is planned to recruit approximately 1500 patients at approximately 250 clinical sites in the US for this study. See Section 8.2 for a discussion of sample size. Patients will be enrolled in this multi-center, outpatient study by gastroenterologists, family practitioners, internists and general medicine practitioners who have been qualified as Investigators. The study will end when its enrollment, regulatory and study drug exposure objectives have been met. Consequently, not all enrolled patients will receive 53 weeks of treatment.

3 STUDY POPULATION

The study population consists of male and female adult patients with Irritable Bowel Syndrome with Constipation (IBS-C). Patients must meet all of the study entry criteria listed below to be enrolled.

Every effort should be made to ensure that the patient's participation in this trial begins as soon as participation in the plecanatide ("core") study SP304203-04 or SP304203-05 has ended. Ideally, the first visit of this trial (SP304203-06) will occur on the same day as the core study's end-of-study visit (Visit 6) for patients completing the study. For qualifying screen-failure patients, the first visit of this trial will also ideally occur on the same day as the core study's Visit 2. For qualifying patients that withdrew early due to lack of efficacy, the first visit of this trial will also ideally occur on the same day as the core study's EW Visit. In addition, plecanatide study-naïve patients and patients that participated in the Phase 2 study SP304-20212 will be considered for enrollment after completing screening to determine eligibility.

3.1 Inclusion Criteria

Patients with documented diagnosis of IBS-C must meet ONE of the following:

1. Completed plecanatide study SP304203-04 or SP304203-05, were compliant with the previous study's requirements, and did not experience any Serious Adverse Event (SAE) deemed related to study drug during the course of the previous study.
2. Failed screening in study SP304203-04 or SP304203-05 due to diary noncompliance (exclusion criterion 24 of the core study) or due to another reason, and in all cases, is allowed to enter this study by notification from Sponsor or delegate; confirmation of active IBS-C via ROME III modular questionnaire is required.
3. Withdrawn early from SP304203-04 or SP304203-05 due to lack of efficacy and completed an early withdrawal visit (Visit EW) in the core study.
4. Completed plecanatide study SP304-20212
5. Completed an early withdrawal visit in SP304-20212 study and reason for withdrawal was not a drug related AE
6. Never participated in a plecanatide study (plecanatide study-naïve patient) 18 to 85 years of age (inclusive) with IBS-C as defined by Rome III criteria (See ROME III modular questionnaire for IBS in Appendix 2).

Note: Details of how to use the Rome III questionnaire and the scoring system is provided in Appendix 2. At the clinical site patients will be given simple instructions on how to complete the form only; authorized personnel will review them for completeness only, to ensure that all questions have been answered. At no time will study staff correct or suggest changes of patient entries. The patient-reported responses to the questionnaire will be reviewed by the investigator or designee, who will use the scoring table provided in Appendix 2 for documentation of patients' eligibility. The questionnaire and the scoring chart will be kept as part of the patient's source documents.

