Number of Patients and Population	
Up to 1500 male and female patients with IBS-C who are either:
 
1) Study Completers - completed phase 3 double-blind plecanatide study SP304203-04 or SP304203-05 and did not experience a Serious Adverse Event deemed related to study drug, or
 
2) Eligible Screen Failures - failed screening in study SP304203-04 or SP304203-05 due to diary noncompliance (exclusion criterion 24 of the core study) or due to another reason, and in all cases, is allowed to enter this study by notification from Sponsor or delegate; confirmation of active IBS-C via ROME III modular questionnaire is required.
 
3) Early withdrawal from SP304203-04 or SP304203-05 due to lack of efficacy and completed an early withdrawal visit (Visit EW).
 
4) Patient completed plecanatide study SP304-20212, i.e, had an End-of-Study Visit and did not experience a Serious Adverse Event deemed related to study drug, or
 
5) Patient was randomized and did not complete study SP304-20212, but
 
 (a) completed an early withdrawal visit, and (b) did not have an SAE and (c) the reason for early withdrawal was not a drug-related AE and (d) is allowed to enter this study with written approval from Sponsor or delegate 
6) Plecanatide study-naïve Patients – patients that did not previously participate in any plecanatide study

Study Termination	The study will end when its enrollment, regulatory and study drug exposure objectives have been met. Consequently, not all enrolled patients will receive 53 weeks of treatment.
Study Drug	Plecanatide 6 mg tablets
Rescue Medication	Bisacodyl (Dulcolax [®]) 5 mg tablets
Treatment Duration	Up to 53 weeks (1 year)
Study Design	This is a phase 3, multicenter, open-label, long-term safety and tolerability study of 6 mg daily dose of plecanatide administered orally. Patients who are Study Completers or Eligible Screen Failures whose eligibility is confirmed at the end of their participation in the double-blind plecanatide studies SP304203-04 or SP304203-05 will, ideally, start participation in this open-label trial on the day of or within 4 weeks of last dose of study drug in SP304203-04 or SP304203-05 or, for eligible screen failures, on the day of or within 4 weeks of the end of their

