3.2 Exclusion Criteria

For patients entering from one of the core studies presence of any of the following will exclude the patient from enrollment:

1. Patient is unwilling or unable to: participate in the study for the required duration, understand and sign the informed consent form (ICF) and undergo all protocol related tests and procedures throughout the study.
2. Female patient of childbearing potential with a positive urine pregnancy test on Day 1.

3. Male and female patients of childbearing potential who do not agree to continue to use the method of birth control used in the core double-blind plecanatide study or another acceptable form of birth control for the duration of this clinical trial.
4. Patient has experienced a significant negative change in health status during the course of participation in the core double-blind plecanatide study or after completion of the study.
Note: Any question or concern with regard to a patient's general health status or a potentially significant change in the patient's general health status during their participation in study SP304203-04 or SP304203-05 should be referred to the Medical Monitor for a medical opinion as to the suitability of the patient for participation in this clinical trial.
5. In the opinion of the Investigator or Medical Monitor, it is not in the patient's best interest to participate in the study. The reason(s) for the patient's exclusion must be specified.
6. Use of Linzess® (linaclotide) or Amitiza® (lubiprostone) within 15 days of the Baseline Visit.
7. Patient has not met the colonoscopy requirements outlined by the AGA Institute for his or her particular risk group as they relate to colon cancer screening and/or surveillance. (See Appendix 3)

For plecanatide study-naïve patients and patients that participated in SP304-20212 presence of any of the following will exclude the patient from enrollment:

1. Patient is unwilling or unable to: participate in the study for the required duration, understand and sign the informed consent form (ICF), and undergo all protocol related tests and procedures throughout the study.
2. Female patient is of childbearing potential with a positive urine pregnancy test on Day 1
3. Female patient is lactating.
4. Male and female patients of childbearing potential who do not agree to continue to use an acceptable method of birth control for the duration of this clinical trial.

Acceptable methods of birth control include:

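### Patients who left a core study for lack of efficacy face no stated bar for a prior drug-related SAE, and the prior-SAE conditions for SP304-20212 patients differ between synopsis and Section 3.1

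*Combined protocol and SAP*

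**What the plan says.** Section 3.1 of the protocol states "Patients with documented diagnosis of IBS-C must meet ONE of the following" and then lists six routes. A condition written into one route therefore does not carry over to another.

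- Route 1 covers completers of SP304203-04 or SP304203-05. Among other things, it requires that they "did not experience any Serious Adverse Event (SAE) deemed related to study drug during the course of the previous study".
- Route 3 covers early withdrawals from the same two studies: "Withdrawn early from SP304203-04 or SP304203-05 due to lack of efficacy and completed an early withdrawal visit (Visit EW) in the core study". It contains nothing else.
- Routes 4 and 5 cover SP304-20212. Route 4 asks only for completion. Route 5 asks for an early withdrawal visit and a withdrawal reason other than a drug-related AE.

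The synopsis (Number of Patients and Population) repeats the contrast for the core studies. Its item 1 takes patients who "completed phase 3 double-blind plecanatide study SP304203-04 or SP304203-05 and did not experience a Serious Adverse Event deemed related to study drug", and its item 3 has no SAE wording. For SP304-20212 it says more than Section 3.1. Completers qualify if they "had an End-of-Study Visit and did not experience a Serious Adverse Event deemed related to study drug", and early withdrawals must meet, among other conditions, "b) did not have an SAE".

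None of the seven exclusions for core patients in Section 3.2 names an SAE or relatedness to study drug.

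**The concern.** Two patients in the same core study could have the same related SAE and be treated differently on entry. The one who finished is barred by the text. The one who stopped for lack of efficacy is not. Under Sections 3 and 5.1 the second patient's first visit would ideally fall on the day of the core study's early withdrawal visit, and dosing may last up to 53 weeks. The primary objective is long-term safety, so who may enter after a related SAE matters both for the patient and for what the safety data represent. No reason is given for treating the two groups differently.

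The mismatch for SP304-20212 adds a practical problem. A site working from Section 3.1 and a site working from the synopsis would apply different rules to the same patient.

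**Working it through.** No sample-size or error-rate arithmetic applies. The check is a comparison of texts.

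**Step 1. Prior-SAE condition by previously randomised group**

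| Group | Synopsis | Section 3.1 |
|---|---|---|
| Core completers (item 1) | No related SAE | No related SAE |
| Core early withdrawals, lack of efficacy (item 3) | None | None |
| SP304-20212 completers (item 4) | No related SAE | None |
| SP304-20212 early withdrawals (item 5) | No SAE of any kind | None (withdrawal reason only) |

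The synopsis sets a condition for 3 of 4 groups, and the exception is core early withdrawals. Section 3.1 sets one for 1 of 4. The two places agree on core early withdrawals and disagree on both SP304-20212 groups. Routes 2 and 6 (core screen failures and study-naïve patients) are left out because those patients were not randomised.

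**Step 2. Does the withdrawal reason already settle SAE history?** The synopsis suggests not. For SP304-20212 early withdrawals it lists absence of an SAE separately from the requirement that the reason was not a drug-related AE. If an unrelated withdrawal reason were enough, the first condition would be unnecessary. Section 7.3.1 illustrates how the two can coexist. In this study, ALT or AST above 5 times ULN counts as an SAE, and the Medical Monitor is to be consulted before a patient is withdrawn for it. Such an event need not end treatment. The core studies' own SAE definitions are not in the documents, so this is an illustration only.

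**Step 3. Does another provision close the gap?**

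- Exclusion 4 for core patients applies where "Patient has experienced a significant negative change in health status during the course of participation in the core double-blind plecanatide study" or afterwards. It needs a judgement and does not name SAEs.
- Exclusion 5 is the opinion of the Investigator or Medical Monitor on the patient's best interest.
- Under Section 1, sites learn of eligible early withdrawals through IWRS, the Medical Monitor or a designee. That notice concerns patients who already meet the eligibility criteria and adds no SAE test.
- Section 5.2.2 sends core-study AEs to medical history. That is recording, not an eligibility check.
- The synopsis and Section 5.2.5 bar patients who stop prematurely from later plecanatide studies. Read as covering the core studies, this would cancel route 3, so it must refer to withdrawal from this study.
- For SP304-20212 patients, the separate list in Section 3.2 also names no prior SAE. Its items 5 and 11 (best interest, pre-existing conditions) again rest on judgement.

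**Step 4. Length of exposure.** 53 × 7 = 371 days, which agrees with Section 9.9.

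**The case against.** The strongest reply is that the gap is narrow and partly guarded. Exclusion 4 looks back over the whole core study, so a resolved event can still count. An SAE is serious by definition, and the note to exclusion 4 sends any doubt about health status to the Medical Monitor. Early withdrawals also pass through a notification step that Section 1 does not require of completers. Synopsis and Section 3.1 agree on item 3, so the difference may be intended. All of this limits the consequence. It does not remove the gap, because exclusions 4 and 5 apply equally to completers, who were still given an explicit bar, and no rationale for the difference is stated.

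Four stronger readings are tempting, and the documents do not support them.

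- *A reader might infer that such a patient will be admitted.* Entry is not automatic, since the Investigator or Medical Monitor may refuse.
- *A reader might infer that the patient is necessarily re-exposed.* The core studies are double-blind, and the patient may have received placebo.
- *A reader might infer that the safety dataset otherwise excludes patients with a prior related SAE.* Under Section 3.1, routes 4 and 5 carry no SAE condition either.
- *A reader might infer a frequency from Section 2.1.3.* No treatment-related SAE is reported in the Phase 2 IBS-C study, where 342 patients received plecanatide. The one-sided 95% upper bound is 1 − 0.05^(1/342) = 0.87%, about 1 in 115. Adding the plecanatide patients in three other studies with no related SAE (712, 58 and 53) gives 0 of 1,165 and a bound of 1 − 0.05^(1/1165) = 0.26%, about 1 in 390. Neither figure describes core-study patients who withdrew for lack of efficacy. Doses and populations differ, and that group may include placebo patients.

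**Conclusion.** The point holds as an inconsistency in the entry criteria that should be resolved. A patient with a drug-related SAE in SP304203-04 or SP304203-05 who withdrew for lack of efficacy is not explicitly barred and could receive plecanatide for up to 53 weeks. Separately, Section 3.1 drops the SAE conditions that the synopsis sets for both SP304-20212 groups.

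The case is expected to be rare, because it needs a related SAE together with lack of efficacy as the recorded withdrawal reason. The documents give neither the frequency of that combination nor the number of lack-of-efficacy withdrawals, so its size cannot be stated. The conclusion rests on the literal text of the entry routes. It assumes that no eligibility instruction outside these documents, such as an IWRS specification, supplies the missing condition.

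**What to change.** Reconcile the prior-SAE condition across all four previously randomised routes in the synopsis and in Section 3.1. Core early withdrawals and SP304-20212 patients should be handled consistently with core completers, or the protocol should state why a group differs. Changing item 3 alone would leave items 4 and 5 in conflict. A single statement covering every previously randomised patient, referenced from both places, would prevent the two texts from diverging again. Which condition applies is the sponsor's clinical decision.

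The cost is a short amendment to two sections. Possibly a few patients become ineligible, out of about 1500 planned (Section 2.6). For the core studies, AE data recorded there are already drawn on at entry to this study (Section 5.2.2), so little new data collection should be needed.

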3.2 Exclusion Criteria

For patients entering from one of the core studies presence of any of the following will exclude the patient from enrollment:

1. Patient is unwilling or unable to: participate in the study for the required duration, understand and sign the informed consent form (ICF) and undergo all protocol related tests and procedures throughout the study.
2. Female patient of childbearing potential with a positive urine pregnancy test on Day 1.

3. Male and female patients of childbearing potential who do not agree to continue to use the method of birth control used in the core double-blind plecanatide study or another acceptable form of birth control for the duration of this clinical trial.
4. Patient has experienced a significant negative change in health status during the course of participation in the core double-blind plecanatide study or after completion of the study.
Note: Any question or concern with regard to a patient's general health status or a potentially significant change in the patient's general health status during their participation in study SP304203-04 or SP304203-05 should be referred to the Medical Monitor for a medical opinion as to the suitability of the patient for participation in this clinical trial.
5. In the opinion of the Investigator or Medical Monitor, it is not in the patient's best interest to participate in the study. The reason(s) for the patient's exclusion must be specified.
6. Use of Linzess® (linaclotide) or Amitiza® (lubiprostone) within 15 days of the Baseline Visit.
7. Patient has not met the colonoscopy requirements outlined by the AGA Institute for his or her particular risk group as they relate to colon cancer screening and/or surveillance. (See Appendix 3)

For plecanatide study-naïve patients and patients that participated in SP304-20212 presence of any of the following will exclude the patient from enrollment:

1. Patient is unwilling or unable to: participate in the study for the required duration, understand and sign the informed consent form (ICF), and undergo all protocol related tests and procedures throughout the study.
2. Female patient is of childbearing potential with a positive urine pregnancy test on Day 1
3. Female patient is lactating.
4. Male and female patients of childbearing potential who do not agree to continue to use an acceptable method of birth control for the duration of this clinical trial.

Acceptable methods of birth control include:

- a. Hormonal contraceptive (e.g., oral contraceptive, implanted or injected hormonal contraceptive) at least 2 months prior to enrollment.
- b. Use of double-barrier contraception (e.g., condom plus diaphragm, spermicide or intrauterine device).
- c. Surgical sterilization (men who have had a vasectomy or women with bilateral oophorectomy, hysterectomy or tubal ligation).
- d. Maintain a monogamous relationship with someone who is surgically sterile or is not of childbearing potential (e.g., post-menopausal).
- e. Note: Abstinence is not considered an acceptable form of contraception for the purposes of this study.

Post-menopausal is defined as without menses for at least 12 consecutive months before screening and have an elevated Follicle-Stimulating Hormone (FSH) consistent with menopause.

Women who are still menstruating must be able to differentiate their abdominal symptoms associated with IBS-C from those associated with their menses.

5. In the opinion of the Investigator or Medical Monitor, it is not in the patient's best interest to participate in the study. The reason(s) for the patient's exclusion must be specified.
6. Use of Linzess® (linaclotide) or Amitiza® (lubiprostone) within 15 days of the Baseline Visit.
7. Patient reports participation in a clinical study or use of an investigational drug treatment within 30 days of Screening. Participation in an observational study (i.e., registry where no study drug is administered) will be allowed.

8. Patient has a BMI < 18 or > 40 kg/m².
9. Patient has not met the colonoscopy requirements outlined by the AGA Institute for his or her particular risk group as they relate to colon cancer screening and/or surveillance (See Appendix 3).
10. Patient has unexplained and clinically significant "alarm symptoms" such as lower GI bleeding, iron-deficiency anemia, weight loss or systemic signs of infection.
11. Patient has any pre-existing medical condition (based on medical history or PE or laboratory evaluations) that is considered clinically significant enough to potentially interfere with study assessments or the patient's participation in and completion of the study. The Investigator must get approval from the Sponsor's Medical Monitor or designee before randomizing any patient who has what the Investigator considers clinically-significant medical history, signs, symptoms, or test results during the Screening Period of the study. These include but are not limited to:
 - a. History of or current clinically significant cardiovascular, nervous system, pulmonary, renal, hepatic, endocrine or gastrointestinal disease. Gastrointestinal diseases and conditions include inflammatory disorders (e.g., ulcerative colitis or Crohn's Diseases), familial adenomatous polyposis, structural abnormality of the GI tract that can affect GI motility or defecation, surgery to remove or bypass any portion of the GI tract
 - b. History of or current cancer (other than basal cell or squamous cell carcinoma of the skin) unless the malignancy has been in a complete remission without maintenance chemotherapy for at least 5 years prior to Visit 1.
 - c. Any concomitant medical illness that is predominantly characterized by chronic abdominal pain
 - d. Major surgery, i.e., requiring general anesthesia within 6 months of the Screening Visit, or abdominal laparoscopic procedure within 60 days of the Screening Visit.
 - e. Determined at screening visit, patient has any abnormal laboratory value that is considered clinically significant by the Investigator. Any laboratory value that is $\geq 3x$ the upper limit of normal (ULN) must be reviewed for potential clinical significance by the Sponsor's Medical Monitor or designee and cleared for randomization (if otherwise eligible).
12. Current clinically significant active viral hepatitis.
13. History of or infection with HIV.
14. Positive urine screen for opiates

